**Data collection and handling:**

Written recording forms will be marked with an anonymous participant code. Data from recording forms for stage one and stage two will be extracted and inputted into the SPSS statistical analysis package by the PI. Recording forms will be stored in a locked filing cabinet in the SLT NHS office.

Data from participant questionnaires from stage one and stage two will be downloaded from Microsoft Forms into a Microsoft Excel database. All digital database files will be stored on a password-protected NHS laptop. Long-term arrangements: Study documents including data and investigator site files will be archived at the Trust's off site archiving facility following local procedures.

The Vscan Air ultrasound system allows clinicians to securely share data and images and includes sharing auto-anonymized images with other apps, with no cloud requirement.

Images will be stored on a NHS laptop which is password protected and will be stored in a password-protected file.

All data will be anonymised via a combination of identifier as a healthy volunteer (HV) or patient (PT) and participant number, followed by the date of clinic (e.g HV1 18.07.22, or for patients PT118.07.22).

Data for healthy volunteer and patients will be analysed by the Principal Investigator electronically on an NHS laptop.

Advice will be sought from LTHTR research team regarding support for statistical analysis of data, but all patient identifiable data will be removed before this stage.

Research data will be stored electronically, which will comprise scanned consent forms and questionnaires, US and laryngoscopy images, examination data recording sheets and statistical data. Electronic data will be stored on the NHS Trust server in a password-protected folder, accessed only by the Principal Investigator.

Study documents including data and investigator site files will be archived at the Trust's off site archiving facility following local procedures.

Identifiable personal data for the healthy volunteers or the patient participants will not be used for either stage 1 or 2.

Healthy volunteer consent forms and any data will be kept in a separate file, and no access to medical records will be made for these patients. The local SOP for Research with Health Volunteers will be followed.

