## **Proposed methods:**

### **Stage one: healthy controls:**

Volunteers will be recruited from NHS staff at the host organisation (LTHTR). Healthy volunteers will be given an information leaflet and consent form upon providing an expression of interest.

Informed consent will be taken by the PI from healthy volunteers who decide to go ahead. It will be stressed that participation and consent can be withdrawn at any time. The consent process itself will take place before the procedure and will be taken by the PI (CS). Consent will be taken in a separate and private room (either the booking-in room in the endoscopy department at RPH, or a separate clinic room in the chest Clinic). This will be completed before the procedure and before entry into the room where the ultrasound procedure will take place.

The consent forms will be stored in a locked cabinet in PI's office. Longer-term, study documents including data and investigator site files will be archived at the Trust's off site archiving facility following local procedures.

Healthy volunteers will be allocated a time and date to attend Chest clinic, or the Endoscopy department at the host organisation, Royal Preston Hospital (RPH) for the scanning session. The scan will be carried out in a private room using transmission gel. Access only to the neck area is required, with privacy and dignity always respected.

The PI will perform an US scan of the larynx, using the Vscan Air (GE), using a protocol designed by the PI. The scan is recorded and stored securely using GE's system. A proportion of scan will be sent to the study collaborator ([name]) and a Specialist Head & Neck Sonographer securely and anonymously with no patient identifiable information included in order to confirm findings when there is uncertainty, and in order to ensure inter-rater reliability.

The scan will consist of a "sweep" of the larynx to identify the main landmarks (hyoid bone, thyroid cartilage, arytenoid cartilages, vocal cords and false vocal cords). A recording form has been prepared for ease of recording. An anonymised code number will be assigned to the Healthy volunteer.

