### **Stage two: patient population**

A sample of 30 participants will be recruited from consecutive patients referred to our NHS Tertiary Airways service for assessment for complex breathlessness and ILO. Participants will be asked at initial assessment, after they have consented to the laryngoscopy, if they would wish to undergo TLUS concurrently with their usual care of diagnostic laryngoscopy.

An information leaflet will be given, and written consent form completed with the patient by the PI. Written Information will be provided at the point of initial consultation (at least 48 hours before the planned procedure. Written consent will take place at the appointment for the Laryngoscopy (usual care for laryngoscopy), by the PI (CS). A witness will not be present. Consent will take place in a private booking-in room that is part of usual care for patients attending for laryngoscopy assessment for ILO). Patients have more than 48 hours to consider the information and decide if they would like to participate.

Patients who require an interpreter for their initial consultation will be provided with information via the interpreter of the study.

Patients will be informed that usual care will not be affected by their decision to participate or not, and that consent can be withdrawn at any point. If the patient finds dual assessment with laryngoscopy and TLUS too invasive or distressing, they can withdraw consent, and the TLUS will be stopped.

It is envisaged that the TLUS operator (PI) will perform the US assessment whilst another SLT completes the laryngoscopy (usual care) and works through the usual diagnostic laryngoscopy provocation protocol to induce symptoms. The US-operating SLT will take a note of settings to achieve image acquisition and will take note of vocal fold movements on an anonymised recording form with subject allocation number identified.

The SLT operators (TLUS and laryngoscopy) will be blinded to the images and results of the other assessment (either TLUS or laryngoscopy), as the screen for the Laryngoscopy system can be rotated away to be unobservable by the US-operator SLT. Following the procedure, the SLT conducting the US will leave the endoscopy theatre room to allow for usual debrief to occur with the patient (usual care). After this, the patient will be asked to complete a short questionnaire electronically to elicit their experience of TLUS.

<https://forms.office.com/pages/designpagev2.aspx?lang=en->

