### **Data analysis:**

The outcomes of the TLUS and laryngoscopy assessments in stage one and stage two and will be analysed using SPSS. 2 x 2 tables will be generated to calculate values of sensitivity (whether a participant can be confirmed as having ILO, or mimicked ILO) and specificity (whether ILO, or mimicked ILO, can be ruled out for a participant), and confidence intervals for visualisation of the vocal folds using TLUS. In stage two, percentage agreement between TLUS and laryngoscopy for confirmation or non-confirmation of ILO will also be calculated.

The values, if available, for measurements of the distance between the arytenoids for healthy volunteers and patients during normal breathing, deep inspiration, and during ILO (mimic in stage 1 and actual in stage 2), will be analysed via a non-parametric comparison of means within SPSS.

Quantitative questionnaire data will be analysed using Microsoft Excel to generate mean values and ranges. Qualitative questionnaire data will be analysed using thematic analysis (Braun and Clarke, 2006), with themes generated to aid understanding of participants' experiences of the TLUS and laryngoscopy procedures.

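### Nothing masks the reading of arytenoid distances to group, and the participant code shows volunteer or patient status, so a volunteer-patient comparison of those distances is open to reader bias

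*Combined protocol and SAP*

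**What the plan says.** All references are to the combined protocol and SAP.

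- **Code.** Data collection and handling: "All data will be anonymised via a combination of identifier as a healthy volunteer (HV) or patient (PT) and participant number". The code ends with the day of the visit, as the examples given there show. The same section applies the code to the paper forms: "Written recording forms will be marked with an anonymous participant code".
- **Scanning.** Stage one: "The PI will perform an US scan of the larynx". Stage two: "It is envisaged that the TLUS operator (PI) will perform the US assessment whilst another SLT completes the laryngoscopy".
- **Analysis.** Data collection and handling: "Data for healthy volunteer and patients will be analysed by the Principal Investigator electronically on an NHS laptop".
- **Blinding.** The stage two section says that the two operators "will be blinded to the images and results of the other assessment (either TLUS or laryngoscopy"). No section mentions masking to volunteer or patient status.
- **Second reading.** The stage one section sends some scans, without identifying details, to a collaborator and a specialist sonographer. The purposes are to settle uncertain findings and to check inter-rater reliability.
- **Endpoint.** Data analysis covers "measurements of the distance between the arytenoids for healthy volunteers and patients" in normal breathing, deep inspiration and ILO (mimicked in stage one, actual in stage two). It is conditional on the values being available and uses a non-parametric comparison in SPSS. It names neither the measurer nor the contrast to be tested.

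**The concern.** Measuring a distance on a moving ultrasound image means choosing a frame and placing two calipers, and both are matters of judgement. If the reader knows whether the clip comes from a volunteer or a patient, a small unconscious shift in those choices appears as a group difference. It cannot be separated from a true difference afterwards without re-reading.

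The measurements bear on stated aims. The range of vocal fold movement in volunteers and patients is listed among the primary aims, and closure measurements associated with a positive ILO diagnosis among the secondary aims. A reading shift could carry into any reference values that later work takes from this pilot. Calling the data anonymised protects identity, but it does not mask the group.

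**Working it through.** The documents give no power, significance level, SD or effect size for the distances, so there is no figure to reproduce. The check has two parts.

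**1. Who can know the group at each step**

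| Step | Who, per the documents | Group known? |
|---|---|---|
| Scan, stage one | Principal investigator | Yes, from being present |
| Scan, stage two | Principal investigator (as envisaged) | Yes, a laryngoscopy is under way |
| Recording form | Carries the code | Yes, from HV/PT |
| Distance measurement | Not named; live or from recordings not stated | Yes, if the scanner measures or the code is visible |
| Second reading of some scans | Collaborator and sonographer | Unclear; depends on whether the code travels with the files |
| Analysis | Principal investigator | Yes |

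The stage two blinding separates TLUS from laryngoscopy within a patient during the procedure. It does nothing for volunteer versus patient. The two sets of results are compared after the clinical session, so a later distance reading is not protected from the laryngoscopy result either.

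Masked reading looks feasible. The stage one section says that scans are recorded and stored. It also fixes the order of commands, because the recordings have no sound, so that each movement can be told apart in analysis. Both points suggest later review of recordings.

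**2. What a reading shift would do (illustration only)**

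Inputs: 30 patients, from the stage two section. Assumed, because the documents do not state them: 10, 20 or 30 volunteers; two-sided 5% level; normal data; no true difference; a constant reader shift of δ SD in one group. The test is Mann-Whitney, as the plan asks for a non-parametric comparison. Simulated rejection rates (4,000 runs each):

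| Volunteers | δ = 0 | δ = 0.25 | δ = 0.5 |
|---|---|---|---|
| 10 | 4.4% | 9.4% | 24.8% |
| 20 | 5.0% | 12.3% | 37.0% |
| 30 | 5.6% | 13.9% | 44.2% |

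A repeat with 10,000 runs gave about 9, 12 and 15% at 0.25 SD and about 24, 38 and 44% at 0.5 SD.

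Closed-form check for a comparison of means: λ = δ·√(n₁n₂/(n₁+n₂)), and the rejection rate is about Φ(λ − 1.96).

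- 10 vs 30: √(300/40) = 2.739. λ = 0.685 and 1.369, giving 10.1% and 27.7%.
- 20 vs 30: √(600/50) = 3.464. λ = 0.866 and 1.732, giving 13.7% and 41.0%.
- 30 vs 30: √(900/60) = 3.873. λ = 0.968 and 1.936, giving 16.1% and 49.1%.

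These run a little above the simulated values, as expected: the formula treats the SD as known and the rank test is slightly less efficient.

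**The case against.** The strongest objection is about cause. A reader might infer that the code is what unmasks the measurement. The documents do not support that: the principal investigator knows the group from doing the scans, and a neutral label would change nothing at acquisition. This stands. The code matters for reading from stored clips and for the second readers. Even for them the documents leave room for doubt, because they mention auto-anonymised image sharing without saying what those files carry.

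A reader might also infer that one person is stated to scan, measure and analyse while expecting a particular result. The plan names no measurer and gives no directional hypothesis. If distances are taken live, clip labels are irrelevant. It is fair to presume that the principal investigator measures, since other readers are named only for some of the scans, but this remains an inference.

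The comparison is also uncertain. The distances are conditional on availability, and the contrast could be between groups or between breathing conditions. A within-person contrast would not be affected by knowledge of group in the same way. The concern therefore applies only if distances are obtained and the groups are compared.

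Finally, the second reading is a partial safeguard. It covers some scans only, and nothing says that those readers are masked to group.

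**Conclusion.** The point holds in limited form. The code shows the group, the principal investigator is planned to scan and analyse both groups, and no section provides for distances to be read masked to group. A volunteer-patient comparison of those distances is open to reader bias, and the present coding rule closes off the simplest protection.

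The error rates (about 9-15% at 0.25 SD, about 24-44% at 0.5 SD) rest on an assumed shift and an assumed stage one size. They show what a bias of that size would do. They are not an estimate for this study, because the documents give no basis for the size or direction of any shift.

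The point also does not extend to sensitivity and specificity in stage two. Those rest on the blinding between TLUS and laryngoscopy operators, which is a separate matter. This is a worthwhile improvement to a pilot, not a flaw that invalidates it.

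**What to change.** 1. For distance measurement, cut stored clips by breathing condition and give each a random neutral number with no HV/PT prefix and no date. Hold the link in a separate key file.
2. Read the clips from both stages in one mixed, random-order batch after recruitment ends. Merge group and laryngoscopy result only when the distances are locked.
3. Send the second readers their clips under the same neutral numbers.
4. Keep the after-session comparison of TLUS and laryngoscopy for ILO yes/no separate from the distance file, so that it can go ahead as planned.
5. State in Data analysis who measures the distances, from what material, and which contrast is tested.

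Cost: a random list, a key file, time to cut the clips, and later measurement. No extra reader is required, though one who did not scan would strengthen the masking. Masking stays partial, because the principal investigator acquired the scans and the manoeuvres differ between stages, so clip content may give the group away. The change does not remove real differences between the groups in setting or in mimicked versus actual ILO. It has to be in place before the distances are read; after that, only a full re-reading would help.

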### **Primary aims:**

To perform analysis of the range of vocal fold movements on inspiration, using TLUS in healthy volunteers and patients referred to a tertiary airways service.

To assess the sensitivity, specificity and positive predictive value of the use of ultrasound in the assessment of ILO, using Laryngoscopy as reference standard.

To investigate the patient and healthy volunteer perspectives of TLUS assessment of the vocal cords.

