A record will be taken of the frequency in MHz and depth that successful visualisation of the vocal cords occurred to help inform future studies and refine the protocol. Any other factors that are deemed useful to include to help replicate findings and improve image quality and scanning success will also be recorded (such as gain used, high or low, and approach transverse, or lateral longitudinal, and the use of any pre-sets such as Neo-head, lung or small parts).

When the vocal cords are visualised, the healthy volunteer will be asked to breathe normally, take 3 deep inspirations, and then, say “ee” for a sustained period. They will then be asked to breath hold, then take a deep breath in (3 trials), and then mimic ILO (the PI will discuss how to do this before the scan takes place). The commands for each of the above will be in the same order for each patient, as there is no accompanying sound, this will allow for easier analysis to be able to differentiate each vocal cord movement according to what the volunteer was asked to do.

Following the procedure, the volunteer will be given an electronic questionnaire to complete, so that feedback on their experience can be gained and used as part of writing up of findings.

[https://forms.office.com/pages/designpagev2.aspx?lang=en-US&origin=OfficeDotCom&route=Start&subpage=design&id=gmOokJ\\_8nEW5GphS-wiyzcd-VqpQSdVGguxTgVT2MfRUMEZUNUoxT1YyQkIPOEVVM0VQVVpJRUVEUS4u](https://forms.office.com/pages/designpagev2.aspx?lang=en-US&origin=OfficeDotCom&route=Start&subpage=design&id=gmOokJ_8nEW5GphS-wiyzcd-VqpQSdVGguxTgVT2MfRUMEZUNUoxT1YyQkIPOEVVM0VQVVpJRUVEUS4u)

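### As written, the coding rule lets the PI link each experience questionnaire to its author, which leaves a primary aim open to favourable response bias of unknown size

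*Combined protocol and SAP*

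**What the plan says.** Participant experience is one of three primary aims: "To investigate the patient and healthy volunteer perspectives of TLUS assessment of the vocal cords". The instrument is an online form. In stage one, after the scan, "the volunteer will be given an electronic questionnaire to complete". In stage two the patient completes a similar form after the debrief.

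Data collection and handling sets one labelling rule: "All data will be anonymised via a combination of identifier as a healthy volunteer (HV) or patient (PT) and participant number". The rule then appends the clinic date to this code. On the questionnaires the section says: "Data from participant questionnaires from stage one and stage two will be downloaded from Microsoft Forms into a Microsoft Excel database". It also lists "scanned consent forms and questionnaires" among the research data kept in an electronic folder that only the PI can open. On analysis it says: "Data for healthy volunteer and patients will be analysed by the Principal Investigator electronically".

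On the respondents in stage one: "Volunteers will be recruited from NHS staff at the host organisation". Data analysis plans means and ranges for the quantitative answers and thematic analysis for the free text. Study end definition allows the trial to be discontinued if patients report an adverse experience of the ultrasound.

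**The concern.** A rating of a procedure is most useful when the person giving it has no reason to please the person who performed it. Here the operator is also the one who takes consent, holds the records and analyses the answers. If each answer carries a participant number and a clinic date, the operator can trace it. Respondents who know or suspect this may soften criticism, and a member of staff rating a colleague has more reason to do so.

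The bias would run one way, towards concluding that the ultrasound is well tolerated. No independent measure of experience is collected, so later analysis could neither detect nor remove it. At stake is the credibility of one primary aim, and in stage two the patient feedback that can lead to discontinuation.

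**Working it through.** The plan gives no figure on this point, so the check sets its sections side by side.

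1. **Does the rule reach the questionnaires?** Data collection and handling says explicitly that the written recording forms bear a code. It describes the questionnaires separately, as a download from Microsoft Forms to Excel, and mentions no code field. The labelling rule is nevertheless framed to cover all data, and nothing exempts the questionnaires. The natural reading is that they are covered. This is an inference, because the form is not shown.

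2. **Who could make the link?** The PI, in both stages.

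| Step | Stage one | Stage two |
|---|---|---|
| Consent | PI | PI |
| Ultrasound | PI | PI |
| Analysis | PI | PI |
| First approach | Volunteers express interest | Not stated who asks |
| Respondents | Staff of the host Trust | Patients of the airways service |
| Operator away during questionnaire | Not described | Operator leaves, then debrief, then form |
| Feeds the adverse-feedback stop | No (rule names patients) | Yes |

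Stage one consent forms are kept in the PI's office, and the electronic research folder is open to the PI alone.

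3. **Does any planned analysis need the link?** Means, ranges and themes need only the group label. The diagnostic 2 x 2 tables and the arytenoid distances do not use the questionnaires. The secondary aims mention age, gender and scanning approach, but Data analysis does not relate any of these to the ratings. Removing the individual code leaves every planned questionnaire result unchanged.

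4. **How large could the bias be?** The documents give no scale, expected rating or spread, so it cannot be estimated. An illustration with assumed inputs for the 30 stage two patients:
   - Assume 6 of 30 had a poor experience: 6/30 = 20%.
   - If one third of the 6 soften their answer: (6 − 2)/30 = 4/30 = 13.3%.
   - If one half soften it: (6 − 3)/30 = 3/30 = 10%.

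   The Wilson 95% interval for 6/30 is about 10% to 37% (centre (0.2 + 3.84/60)/(1 + 3.84/30) = 0.234, half-width 0.139). Softening of this size would therefore be hard to tell from chance. The plan reports means and ranges rather than this proportion, so the figures show only the direction and the kind of shift.

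**The case against.** The strongest reply is that the plan never states that the form carries a code. Only the paper recording forms are explicitly coded, and the section adds that identifiable personal data will not be used. Response bias also depends on what participants believe. The forms and the information and consent pages are not in the reviewed text, and they may contain an assurance of confidentiality. This stands as a limit: the plan leaves traceability open on its own wording, but it does not show that participants know of it.

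The second reply is that stage two already separates the patient from the operator. That is correct, and it removes most of the face-to-face pressure. It does not remove the link in the records.

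The third is that a link has uses: following up a report of harm, removing answers on withdrawal, or exploratory work in a pilot. The first two are real costs of the fix and are dealt with there. The third is not planned.

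A reader might infer more than the documents support:
- **That the PI recruits everyone.** The plan does not say who first approaches stage two patients. Consent, scanning and analysis by the PI are explicit and are enough for the point.
- **That pressure on colleagues could keep the feedback stop from operating.** Colleagues appear only in stage one, and the stop concerns patients only. It has no stated threshold, so whether softened answers would alter it cannot be assessed.
- **That the poor-experience rate would fall from 20% to 10–13%.** Those figures are assumptions and do not estimate anything in this trial.

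**Conclusion.** The point holds in a limited form. Read as written, the labelling rule covers the questionnaires and lets the operator being rated link each answer to its author, while no planned analysis uses that link. This leaves a primary aim open to favourable bias whose size is unknown and cannot be derived from the documents. The concern is greatest in stage one. It is weaker in stage two, where the operator has left the room but traceability remains.

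The conclusion rests on two assumptions: that the rule applies to the online responses as its wording implies, and that some respondents would answer more freely without a code. It is a cheap improvement to make before data collection and not a fatal flaw in the pilot.

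**What to change.** - **Data collection and handling:** exempt the questionnaire from the coding rule. Responses should carry only 'volunteer' or 'patient', with no name, participant number or clinic date.
- **Stage one: healthy controls:** have volunteers complete the form away from the PI, as stage two already arranges.
- **On the form:** say that no name or participant code is collected. Do not promise that answers are untraceable. Submission times, recognisable free text and interim looks among about 30 patients would make that promise too strong.
- **Download:** take responses in batches, with interim review only for the existing patient-feedback rule under Study end definition.

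The work is a change to the form's settings and a sentence or so in each of two sections, with no added participants, visits or analyses. The cost is that a response can no longer be linked to a scan, removed if consent is withdrawn, or followed up individually. The form should say so and direct participants to report any harm or distress through the usual study contact, so that such reports do not depend on the questionnaire.
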